**OTcF Pre-Defined Thresholds** 

- QTcF > 450 msec
- OTcF > 480 msec
- QTcF > 500 msec
- QTcF increased by > 30 msec from baseline
- QTcF increased by > 60 msec from baseline

All ECG data will be presented in a by-subject listing. Subjects meeting pre-defined threshold values for QTcF will be flagged.

All abnormal ECG data (abnormal not clinically significant and abnormal clinically significant) will be presented in a by-subject listing. Subjects meeting pre-defined threshold values for QTcF will be flagged.

# 8.5 Physical and Neurological Examinations

All physical examination and neurological examination data will be presented in by-subject listings.

# 8.6 Vital Signs and Anthropometrics

CONFIDENTIAL Page 24 of 32

Vital signs data collected include systolic blood pressure (SBP) (mmHg), diastolic blood pressure (DBP) (mmHg), pulse rate (bpm), respiratory rate (breaths/min), oral temperature (C), weight (kg), and BMI (kg/m²) and will be summarized descriptively for continuous data by visit and timepoint for the observed value as well as for the change from baseline value, where available.

A categorical summary table describing the n (%) of subjects meeting the below thresholds at any post-baseline visit/timepoint will be generated.

Vital Sign Pre-Defined Thresholds

- SBP > 180 mmHg (High)
- SBP  $\leq$  90 mmHg (Low)
- DBP > 110 mmHg (High)
- DBP  $\leq$  50 mmHg (Low)
- SBP increased by  $\geq 30$  mmHg from baseline
- SBP decreased by  $\geq 30$  mmHg from baseline
- DBP increased by  $\geq 20$  mmHg from baseline
- DBP decreased by  $\geq 20$  mmHg from baseline

All vital signs data will be presented in a by-subject listing.

# 8.7 Magnetic Resonance Imaging (MRI)

MRI results for subjects where amyloid-related imaging abnormalities (ARIA) are detected will be presented in a by-subject listing.

All centrally read MRI data will be presented in a separate by-subject listing.

# 8.8 Columbia-Suicide Severity Rating Scale (C-SSRS)

C-SSRS questions since last visit will be summarized descriptively.

All C-SSRS data will be presented in by-subject listings.

#### 8.9 Other Measures

Urine drug, urine cotinine and alcohol screening; infectious disease tests; meal consumption data, and serum and urine pregnancy test data will be presented in by-subject listings.

If after the study results are reviewed, or Sponsor recommends additional safety parameters or analyses be completed, they will be fully described and documented in the final clinical study report. The SAP does not need to be amended to complete any other safety measures identified as post-hoc.

# 9 SECONDARY ENDPOINTS ANALYSES

CONFIDENTIAL Page 25 of 32

# 9.1 Serum Pharmacokinetic Analyses

#### 9.1.1 General Considerations

All PK analysis summaries will be presented using the PK Population. PMN310 serum concentration data will be listed by cohort, subject, and visit/sampling time point. Descriptive summary statistics will be provided by cohort and visit/sampling time point.

Any protocol deviations, concomitant medications, or adverse events which could impact PK concentration-data profiles and/or PK parameter estimates will be designated by the Sponsor to indicate whether these PK data should be excluded from analysis. All data that are excluded in this manner will be listed and the reason for exclusion clearly noted. This review will be done by blinded personnel prior to database lock.

Furthermore, subjects must not have quantifiable pre-dose (prior to the start of infusion) concentrations greater than 5% of the corresponding  $C_{max}$ . All PK data excluded in this manner will be evaluated on a case-by-case basis and agreed upon with the Sponsor *a priori*.

Serum concentrations of PMN310 will be measured by validated assays and PK parameters will be estimated using standard Phoenix® WinNonlin® (Version 8.3, Certara USA) non-compartmental analysis (NCA) methods and actual blood sampling times relative to dosing (i.e., relative to the end of infusion). If the actual collection time is unknown, the nominal collection time may be used for the purposes of PK parameter estimation.

For the calculation of summary statistics and graphical displays of serum concentrations (except for plots of geometric mean [geometric CV%]), concentrations that are below the limit of quantification (BLQ) will be set to zero (0) for all measurements. In addition, any quantifiable concentration observed after at least 2 consecutive BLQ values at the end of a profile will be evaluated on a case-by-case basis and may be set to missing along with the BLQ concentrations, if warranted. The number and percentage of values missing and the number and percentage of values BLQ will be presented with the other summary statistics. If >25% of values at a time point within a treatment level are missing or BLQ, no summary statistics will be presented.

Serum concentration data will be summarized descriptively for continuous data by PMN310 dose level and protocol-specified nominal timepoint. Summary statistics for concentration-time data will include: n, mean, standard deviation (SD), coefficient of variation (CV%), minimum, median, maximum, geometric mean, geometric CV%, and the number and percentage of samples that are BLQ and the number and percentage of samples that are missing. All concentration-time data and summary statistics will be reported to the same number of decimal places as displayed in the bioanalytical data, except for CV%, which will be reported to 1 decimal place.

Linear-linear and log-linear mean serum concentration-time vs nominal timepoint plots will also be presented by dose level, while linear-linear and log-linear individual concentration-time vs actual timepoint plots will be presented in a similar manner.

CONFIDENTIAL Page 26 of 32

All serum concentration data (including actual blood sampling times) will be provided in a by subject-listing.

Serum concentration values that are BLQ will also be imputed as follows for the NCA:

- 1. BLQ values at time points prior to any measurable concentration or immediately prior to dosing (pre-dose [prior to the start of infusion]) are imputed as 0.
- 2. BLQ values between two measurable concentrations will be set to the LLOQ/2.
- 3. BLQ values after all measurable concentrations are set to missing.

Serum PK parameters will be summarized descriptively by PMN310 dose level. Summary statistics for the time-related serum PK parameters ( $t_{max}$ ,  $t_{last}$  and  $t_{1/2}$ ) will include: n, mean, SD, median, minimum, and maximum while summary statistics for AUCextrap (%) will include n, number and percentage of subjects with AUCextrap>20%, mean, SD, median, minimum, and maximum. AUC0-\infty values will be considered unreliable estimates if the AUCextrap (%) is greater than 20% and will be excluded from summary statistics but will be listed.

Summary statistics for all other serum PK parameters include: n, mean, SD, CV%, median, minimum, maximum, geometric mean, and geometric CV%.

Except for time-related PK parameters ( $t_{max}$ ,  $t_{last}$ , and  $t_{1/2}$ ), and reporting of CV%, all other PK parameters will be reported to 3 significant digits. For  $t_{max}$ ,  $t_{last}$ , and  $t_{1/2}$ , round all statistics to two decimal places. CV% will be reported to 1 decimal place.

All PK parameter data will be presented in a by-subject listing.

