# 9.1.2 Pharmacokinetic Endpoints

## 9.1.2.1 Serum Pharmacokinetic Parameters

PK parameters will be computed from the individual serum concentrations as data allow.

CONFIDENTIAL Page 27 of 32

PK Parameter	Definition
Study Day 1	
AUC 0-t (AUC last )	Area under the serum concentration-time curve from time zero to the last measurable concentration
$AUC_{0\text{-}\infty}(AUC_{inf})$	Area under the serum concentration-time curve from time zero extrapolated to infinity
AUCextrap	Area under the serum concentration-time curve extrapolated from time t to infinity as a percentage of total area under the concentration-time curve
Cend of infusion	Concentration at the end of the intravenous infusion
$C_{last}$	Concentration corresponding to the time of last measurable concentration ( $t_{last}$ )
$C_{\text{max}}$	Maximum observed serum concentration
$t_{max}$	Time to reach maximum serum concentration
$\mathbf{t}_{\mathrm{last}}$	Time of last measurable concentration
Span	Time interval used to determine $\lambda_Z$ divided by the terminal elimination half-life $(t_{1/2})$
Adjusted r 	Coefficient of determination used as a criteria for the goodness-of-fit measurement of a regression analysis
$t_{1/2}$	Terminal elimination half-life
lambda_z $(\lambda_Z)$	Terminal elimination rate constant
CL	Total body clearance after intravenous infusion
Vd	Volume of distribution during the terminal phase

Additional PK parameters may be estimated as appropriate.

All AUCs including  $AUC_{0-t}$  and  $AUC_{0-\infty}$  will be calculated using the linear-up/log-down trapezoidal method, using actual sampling times. Missing concentrations will be treated as missing and excluded from PK analysis except when they occur at pre-dose (prior to the start of infusion), where they will be set to 0.

 $AUC_{0-\infty}$  will be calculated as outlined below:

$$AUC_{0-\infty} = AUC_{0-t} + (C_{last}/lambda_z[\lambda_z]),$$

where Clast (defined as the last measurable concentration) is the last temporal quantifiable serum concentration.

Maximum concentration ( $C_{max}$ ),  $t_{max}$ , and  $t_{last}$  will be obtained directly from experimental observations. If multiple maxima occur at equal concentrations, the first temporal value will be taken.

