The apparent terminal elimination half-life,  $t_{1/2}$ , where evaluable, will be calculated as the natural log of 2 divided by the terminal elimination rate constant,  $\lambda_z$ . The number of data points included in the regression will be determined by visual inspection, but a minimum of 3 data points in the terminal phase, excluding  $C_{max}$ , is required to estimate  $\lambda_z$ . In order for  $\lambda_z$  and  $\lambda_z$  derived

CONFIDENTIAL Page 28 of 32

parameters (AUC0-∞,  $t_{1/2}$ , Vd, and CL) to be reported, the adjusted  $r^2$  value reported in Phoenix® WinNonlin® must be  $\ge 0.8$ .  $t_{1/2}$  should be determined with a span  $\ge 2$ . If this criterion is not met the data will be excluded from descriptive summaries but will be included in the listing of PK parameters and flagged.

Regression parameters for estimation of  $\lambda_z$ , including the number of time points used, time point range used for the regression (minimum time, maximum time), span, and adjusted  $r^2$  will be listed.

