# 9.1.2.2 Dose Proportionality

Dose proportionality will be analyzed using a power model. The natural log-transformed (ln) parameters ( $C_{max}$  and AUCs: AUC0-t and AUC0-∞) will be fit to a linear model estimating the effect of ln(dose) (Gough 1995). The empirical relationship between a PK parameter and dose is in the following equation:

$$PK = e^{\alpha} * (dose)^{\beta}$$

Where PK represents the PK parameter AUCs and  $C_{max}$ . For analysis, this equation is natural log-transformed, obtaining the equation below:

$$InPK = \alpha + \beta * In(dose)$$

The slope  $\beta$  measures the dose-proportionality between dose and the PK parameter.

The confidence interval criteria for assessment of dose proportionality from Smith et al. (2000) will be used to test for dose proportionality. The *a priori* acceptance range for the slope, according to Smith, is given by:

$$1 + In(0.8)/In(r) < \beta < 1 + In(1.25)/In(r)$$

Where 1.25 and 0.8 are the critical *a priori* values suggested by regulatory authorities for any bioequivalence problem after a data log transformation, and r is the ratio of the largest dose to the smallest dose. Dose proportionality can be claimed if the 90% confidence interval for the slope is entirely contained within this *a priori* range.

Dose proportionality will also be explored graphically: regression/scatter plot in the In-In scale for the power analysis.

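### Should subjects with more than 20% extrapolated AUC also be dropped from the CL and Vd summaries and from the AUC0-inf dose-proportionality model?

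*SAP*

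**What the plan says.** Three parts of the SAP bear on this.

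- **9.1.1 General Considerations.** An AUC0-inf value counts as unreliable when AUCextrap "is greater than 20% and will be excluded from summary statistics but will be listed". The number and percentage of subjects above 20% are tabulated. The text then continues: "Summary statistics for all other serum PK parameters include: n, mean, SD, CV%, median, minimum, maximum, geometric mean, and geometric CV"%. CL and Vd fall under that sentence. The section closes with "All PK parameter data will be presented in a by-subject listing".
- **9.1.2.1 Serum Pharmacokinetic Parameters.** AUC0-inf, t1/2, Vd and CL are named together as derived from the terminal slope. They are reported only if the adjusted r-squared is at least 0.8. A span of at least 2 is then asked for t1/2, followed by "If this criterion is not met the data will be excluded from descriptive summaries but will be included in the listing". No formula is printed for CL or Vd.
- **9.1.2.2 Dose Proportionality.** Cmax, AUC0-t and AUC0-inf all enter the power model, with no mention of extrapolation. The decision rule is: "Dose proportionality can be claimed if the 90% confidence interval for the slope is entirely contained within this" range.

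Protocol 9.4.2 names only Cmax and AUClast for dose proportionality. SAP 6.6 plans no formal hypothesis tests.

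**The concern.** If CL is dose divided by AUC0-inf, a subject whose AUC0-inf is rejected has a CL that is simply the reciprocal of the rejected number times dose. The same report could then show different n for AUC0-inf and CL, with the difference made up of values the SAP distrusts. CL and Vd are named secondary endpoints (SAP 4.2.2), and the protocol synopsis says the results will inform dose selection for later studies.

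The power model raises the same doubt. The 20% rule is confined to summary statistics, so on a literal reading flagged values stay in a fit that carries a claim rule.

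The span sentence is also loose. The data it excludes could be t1/2 alone or the whole group of slope-derived parameters, so two programmers could produce different CL and Vd tables.

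**Working it through.** The documents give no figure on this point to reproduce. The half-life, the CVs and the residual error below are assumptions, as are CL = Dose/AUC0-inf and Vd = CL/λz.

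**1. What the text settles.** The sentence on all other parameters says which statistics are printed. AUC0-inf is neither time-related nor AUCextrap, so it takes its own statistics from that sentence. The sentence therefore sets a format and does not show a decision to keep flagged CL and Vd. The SAP is silent on the point.

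**2. When the flag is raised.** Under mono-exponential decline the extrapolated share is 2^(−T/t1/2), where T is the time of the last measurable sample. Setting this to 20% gives t1/2 = T × ln2/ln5.

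- Day 85 (T = 84): 36.2 days
- Day 57 (T = 56): 24.1 days
- Day 43 (T = 42): 18.1 days

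**3. What the span rule leaves if it covers the group.** At span 2 the half-life is half the fitting interval.

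- End of infusion to Day 85: h = 42, share 2^(−84/42) = 25.0%
- Day 8 to 85: h = 77/2 = 38.5, share 2^(−84/38.5) = 22.0%
- Day 15 to 85: h = 70/2 = 35, share 2^(−84/35) = 18.9%, so nothing is left above 20%

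If the rule covers t1/2 only, this limit does not apply.

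**4. Error in CL and Vd.** Let e be the true extrapolated share and let λz be wrong by a factor (1 + d). Relative AUC0-inf is then 1 + e(1/(1 + d) − 1).

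| | d = −0.14 | d = +0.14 |
|---|---|---|
| CL, e = 0.22 | 1/1.0358 − 1 = −3.5% | 1/0.9730 − 1 = +2.8% |
| Vd, e = 0.22 | 0.9654/0.86 − 1 = +12.3% | 1.0278/1.14 − 1 = −9.8% |
| Vd, e = 0 | 1/0.86 − 1 = +16.3% | 1/1.14 − 1 = −12.3% |

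The CL error is small. The Vd error is larger with no extrapolation at all, because the errors in AUC0-inf and λz partly cancel. It reflects the quality of the slope, which the r-squared rule already screens. It gives no ground for excluding Vd on AUCextrap.

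**5. Keeping against excluding.** Simulation: five doses from 175 to 2800 mg, 6 active subjects each, mono-exponential decline, true slope 1, t1/2 CV 30%, CL CV 20%, log residual SD 0.10. λz is fitted to Days 8 to 85, AUC0-t is taken as error-free, and only fits with adjusted r-squared of at least 0.8 are kept. The margin for the slope is ln(1.25)/ln(16) = 0.080.

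| Assumed median t1/2 | 21 d | 28 d | 36 d |
|---|---|---|---|
| Reportable values flagged | 3.6% | 19.7% | 48.8% |
| Error in flagged AUC0-inf, 5th to 95th percentile | −4% to +9% | −6% to +10% | −7% to +11% |
| Bias in geometric mean CL, flagged excluded (correlation −0.7 between log t1/2 and log CL) | +1.1% | +4.8% | +11% |
| Slope with flagged kept, minus true-AUC slope (5th/95th percentile) | ±0.005 | ±0.008 | ±0.013 |
| Conclusion differs from true-AUC fit, flagged kept | 4.1% | 7.7% | 10.8% |
| Conclusion differs from true-AUC fit, flagged excluded | 9.2% | 27.0% | 35.9% |

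With flagged values kept, the bias in geometric mean CL is at most about 0.3%. The slope and conclusion rows take CL as independent of t1/2; with the correlation of −0.7 the kept-value slopes still lie within about ±0.015. At 36 days the median sits on the 36.2-day threshold, so flagging about half the values is built in.

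The fits with and without flagged values reach different conclusions in 9.0%, 24.0% and 31.3% of trials. The comparison with the true AUC shows that this comes mainly from the fit that discards subjects. Proportionality is claimed in 37.7%, 35.5% and 32.8% of trials with flagged values kept, and in 34.8%, 21.2% and 5.3% without them.

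**The case for a change.** The best case for a change is that the scope of both rules should be fixed before unblinding, because the proportionality rule leads to a claim and listings do not say which analysis was planned. It would cost a few sentences. The simulation is also kind to kept values: it assumes a log-linear terminal phase and an error-free AUC0-t.

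A harder case is a systematic error at one end of the dose range, for example if the lowest dose falls below quantification early. If AUC0-inf in the lowest of five cohorts were biased upward by 10%, the slope would move by −0.028, which is 34% of the 0.080 margin. A 20% bias would move it by −0.053, or 65%.

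The point about scope stands as missing detail. The harder case does not favour exclusion. With 25% extrapolated, λz would have to be 0.7 of its true value across the whole cohort to bias AUC0-inf by 11%. A filter would then remove most or all of the cohort that anchors the low end of the regression. Nor would a second, filtered fit settle the matter. It would be the noisier of the two, while the AUC0-t model, which needs no extrapolation, is already planned beside it.

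**Conclusion.** No change is needed. The SAP does leave open whether the 20% and span rules reach CL, Vd and the AUC0-inf model. A PK analyst can settle that when the outputs are specified, and the literal reading, which keeps the values, is sound. Under the stated assumptions it leaves geometric mean CL within about 0.3% of truth and slopes within about 0.015 of the true-AUC slope. Extending the exclusion would remove slow eliminators selectively and lose precision, with no gain shown.

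The reach is limited as well. Cmax and AUC0-t, the protocol's own proportionality parameters, are untouched, no formal testing is planned, and subjects above 20% are counted and listed.

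The conclusion rests on the standard formulas for CL and Vd, a log-linear terminal phase, and half-lives and variances that the documents do not give. Whether any subject will exceed 20% cannot be known from them.

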# 9.1.2 Pharmacokinetic Endpoints

## 9.1.2.1 Serum Pharmacokinetic Parameters

PK parameters will be computed from the individual serum concentrations as data allow.

CONFIDENTIAL Page 27 of 32

PK Parameter	Definition
Study Day 1	
AUC 0-t (AUC last )	Area under the serum concentration-time curve from time zero to the last measurable concentration
$AUC_{0\text{-}\infty}(AUC_{inf})$	Area under the serum concentration-time curve from time zero extrapolated to infinity
AUCextrap	Area under the serum concentration-time curve extrapolated from time t to infinity as a percentage of total area under the concentration-time curve
Cend of infusion	Concentration at the end of the intravenous infusion
$C_{last}$	Concentration corresponding to the time of last measurable concentration ( $t_{last}$ )
$C_{\text{max}}$	Maximum observed serum concentration
$t_{max}$	Time to reach maximum serum concentration
$\mathbf{t}_{\mathrm{last}}$	Time of last measurable concentration
Span	Time interval used to determine $\lambda_Z$ divided by the terminal elimination half-life $(t_{1/2})$
Adjusted r 	Coefficient of determination used as a criteria for the goodness-of-fit measurement of a regression analysis
$t_{1/2}$	Terminal elimination half-life
lambda_z $(\lambda_Z)$	Terminal elimination rate constant
CL	Total body clearance after intravenous infusion
Vd	Volume of distribution during the terminal phase

Additional PK parameters may be estimated as appropriate.

All AUCs including  $AUC_{0-t}$  and  $AUC_{0-\infty}$  will be calculated using the linear-up/log-down trapezoidal method, using actual sampling times. Missing concentrations will be treated as missing and excluded from PK analysis except when they occur at pre-dose (prior to the start of infusion), where they will be set to 0.

 $AUC_{0-\infty}$  will be calculated as outlined below:

$$AUC_{0-\infty} = AUC_{0-t} + (C_{last}/lambda_z[\lambda_z]),$$

where Clast (defined as the last measurable concentration) is the last temporal quantifiable serum concentration.

Maximum concentration ( $C_{max}$ ),  $t_{max}$ , and  $t_{last}$  will be obtained directly from experimental observations. If multiple maxima occur at equal concentrations, the first temporal value will be taken.

The apparent terminal elimination half-life,  $t_{1/2}$ , where evaluable, will be calculated as the natural log of 2 divided by the terminal elimination rate constant,  $\lambda_z$ . The number of data points included in the regression will be determined by visual inspection, but a minimum of 3 data points in the terminal phase, excluding  $C_{max}$ , is required to estimate  $\lambda_z$ . In order for  $\lambda_z$  and  $\lambda_z$  derived

CONFIDENTIAL Page 28 of 32

parameters (AUC0-∞,  $t_{1/2}$ , Vd, and CL) to be reported, the adjusted  $r^2$  value reported in Phoenix® WinNonlin® must be  $\ge 0.8$ .  $t_{1/2}$  should be determined with a span  $\ge 2$ . If this criterion is not met the data will be excluded from descriptive summaries but will be included in the listing of PK parameters and flagged.

Regression parameters for estimation of  $\lambda_z$ , including the number of time points used, time point range used for the regression (minimum time, maximum time), span, and adjusted  $r^2$  will be listed.

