- PK serum sampling
- Review of concomitant medications
- AE assessment

6.2.2.5. Day 57

On Day 57 (± 3 days), subjects will undergo the following assessments:

- C-SSRS (Since Last Visit version)
- Vital signs
- Clinical laboratory tests:
 - Blood chemistry and hematology
 - Urinalysis
 - Coagulation
- PK serum sampling
- ADA serum sampling
- Note: Residual and unused serum and CSF (if applicable) samples will be stored for future use for the measurement of biomarkers Possible LP. INR/ PT/PTT and platelet results within 2 days prior to the LP must be confirmed and determined to be within normal range before LP.
 - Post LP, subjects will remain supine for a minimum of 4 hours, and may be kept longer for observation at the discretion of the Investigator. After the 4-hour observation period, safety and tolerability will be assessed and subjects will be discharged home
- Review of concomitant medications
- AE assessment

6.2.2.6. Day 85

On Day 85 (± 4 days), subjects will undergo the following assessments:

- C-SSRS (Since Last Visit version)
- Symptom directed physical examination
- Neurologic examination
- Vital signs
- Weight
- 12-lead ECG
- Pregnancy test (non-post-menopausal women only)
- Urine drug, urine cotinine, and serum alcohol screen

- Clinical laboratory tests:
 - Blood chemistry and hematology
 - Urinalysis
 - Coagulation
- PK serum sampling
- ADA serum sampling
- Note: Residual and unused serum and CSF samples (if applicable) will be stored for future use for the measurement of biomarkers Possible LP. INR/ PT/PTT and platelet results within 2 days prior to the LP must be confirmed and determined to be within normal range before LP.
 - Post LP, subjects will remain supine for a minimum of 4 hours, and may be kept longer for observation at the discretion of the Investigator. After the 4-hour observation period, safety and tolerability will be assessed and subjects will be discharged home
- Review of concomitant medications
- AE assessment

6.2.3. Optional Follow-Up Visit – Day 120

The Day 120 visit (\pm 7 days) is optional. Subjects who elect to participate in the Day 120 visit will undergo the following assessments:

- PK serum sampling
- ADA serum sampling
- Note: Residual and unused serum samples will be stored for future use for the measurement of biomarkers

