-  Symptom directed physical examination and neurological examination will be performed at the indicated timepoints.
-  Vital signs should always be collected up to 45 minutes before PK sampling (i.e., nominal time) unless otherwise indicated before infusion, at the end of infusion (see protocol Section 5.2.1 for a definition for complete infusion), and at 0.5, 1, 2, 4, 8, and 12 hours after the end of infusion. Day 2 (24 and 36 hours), D3 (48 hours), and Day 4 (72 hours), Days 8, 15, 29, 43, 85. Subjects should be resting supine for at least 5 minutes before the vital sign assessment; the exact time of assessment is to be recorded.
-  Only subjects ≥ 50 years of age will have MRI assessments at Day 43. If ARIA is detected, repeat MRIs will be performed every 3-4 weeks until ARIA is resolved.
-  ECGs should always be performed up to 45 minutes before PK Sampling (i.e., nominal time) unless otherwise indicated before infusion, at the end of infusion, and at 1, 2, 4, 8, and 12 hours after the end of infusion. Day 2 (24 and 36 hours), D3 (48 hours), and Day 4 (72 hours), , 8, 29, and 85.

CONFIDENTIAL Page 12 of 32

-  Pregnancy test is not required for post-menopausal women. Serum human chorionic gonadotropin at Screening and urinary chorionic gonadotropin thereafter. If a urine pregnancy test is positive, a serum pregnancy test must be obtained. Additional details provided in protocol Section 7.1.9.
-  Pharmacokinetic blood sampling for serum PMN310 concentrations should be performed as follows:
  - Day 1: before infusion, at the end of infusion, and at 0.5, 1, 2, 4, 8, and 12 hours after the end of infusion
    - o Acceptable windows for PK sampling are as follows (exact time of PK collection is to be recorded):
      - Pre-dose sample to be collected within 60 minutes prior to dosing
      - 0.5 to 4-hour post-dose samples to be collected  $\pm$  5 minutes
      - 8 to 12-hour post-dose samples to be collected  $\pm$  10 minutes
  - Day 2 (24 and 36 hours)
    - $\circ$  Acceptable window for PK sampling is  $\pm$  30 minutes (exact time of PK collection is to be recorded)
  - Day 3 (48 hours), Day 4 (72 hours) and Day 5 (96 hours)
    - $\circ$  Acceptable windows for PK sampling are  $\pm$  60 minutes (exact time of PK collection is to be recorded)
    - O Day 5 (96) hours does not require inpatient collection
  - Days 8, 15, 29, 43, 57, 85

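### The span ≥ 2 rule caps the summarised half-life at half the fitting window, so if half-lives are long relative to that window the summary is biased downward, with no count of the values removed

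*SAP*

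**What the plan says.** SAP 9.1.2.1 defines span as the time interval used for λz "divided by the terminal elimination half-life". It then says that half-life "should be determined with a span" of at least 2. The consequence of falling short is put this way: "If this criterion is not met the data will be excluded from descriptive summaries". Such values still appear, flagged, in the parameter listing.

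The window is set subject by subject: "The number of data points included in the regression will be determined by visual inspection". At least three terminal-phase points are required, and Cmax may not be one of them. Adjusted r² must be at least 0.8 for λz and the parameters derived from it to be reported.

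The late serum samples in the SAP schedule of assessments (section 5.1) are "Days 8, 15, 29, 43, 57, 85". A Day 120 sample exists, but Protocol 6.2.3 says that the visit "is optional. Subjects who elect to participate in the Day 120 visit". Day 85 is therefore the last sample scheduled for every subject.

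Half-life is a named secondary endpoint (Protocol 2.2.2, SAP 4.2.2). SAP 9.1.1 summarises it by dose with n, mean, SD, median, minimum and maximum. The same section plans a count and percentage of subjects whose extrapolated AUC exceeds 20%, but no such count for span.

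**The concern.** Half-life is the denominator of span. Whether a value enters the summary therefore depends on the value itself, and the dependence runs one way: for a given window, values above a fixed limit go out and values below it stay in. That is truncation from above, not loss at random. The reported mean, median and maximum can then understate how long the antibody persists, and a reader of the table would see only a smaller n. The protocol synopsis says that the study's outcomes will feed dose selection and preliminary power calculations for later studies in patients, so the summarised PK values will be used.

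**Working it through.** **No figure to reproduce.** The documents state no expected half-life, between-subject CV, assay limit or exclusion rate. The cap follows from the schedule. The size of the bias needs assumptions.

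**Step 1: the cap.** With W the fitting window, span = W / t½, so span ≥ 2 is the same as t½ ≤ W/2.

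- Day 8-85: W = 77, cap 38.5 days
- Day 15-85: W = 70, cap 35 days
- Day 29-85: W = 56, cap 28 days
- Day 43-85: W = 42, cap 21 days (Days 43, 57 and 85 are the three-point minimum)
- Day 29-120: W = 91, cap 45.5 days, if the optional sample is taken and quantifiable

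**Step 2: effect on the mean for a common window.** Assume that half-life is lognormal with mean m and coefficient of variation CV. Put σ² = ln(1 + CV²), μ = ln m − σ²/2 and a = (ln(W/2) − μ)/σ. Then

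- proportion excluded = 1 − Φ(a)
- mean of the values kept = m × Φ(a − σ)/Φ(a)

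Worked case, m = 21 days, CV 30%, Day 29-85: σ = √ln 1.09 = 0.2936; μ = 3.0445 − 0.0431 = 3.0014; a = (3.3322 − 3.0014)/0.2936 = 1.127. Excluded: 1 − 0.870 = 13.0%. Mean kept: 21 × 0.798/0.870 = 19.25 days, which is 8.3% low. The median moves from exp(μ) = 20.1 to exp(μ + σΦ⁻¹(0.870/2)) = 19.2 days, 4.7% low. With 6 active subjects per dose, the chance that a cohort loses at least one value is 1 − 0.870⁶ = 57%.

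Bias in the mean, with the proportion excluded in brackets:

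| Window | 14 d, CV 30% | 21 d, CV 30% | 25 d, CV 20% | 28 d, CV 30% |
|---|---|---|---|---|
| Day 8-85 | under 0.1% | −1.4% (1.3%) | −0.7% (1.1%) | −7.3% (10.9%) |
| Day 15-85 | −0.1% (0.1%) | −2.7% (3.0%) | −1.9% (3.6%) | −10.7% (18.2%) |
| Day 29-85 | −0.7% (0.6%) | −8.3% (13.0%) | −8.9% (25.1%) | −20.9% (44.2%) |
| Day 43-85 | −4.8% (6.3%) | −20.9% (44.2%) | −24.7% (78.3%) | −35.8% (79.8%) |
| Day 29-120 | under 0.1% | −0.4% (0.3%) | −0.1% (0.1%) | −3.1% (3.6%) |

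The CV matters as well. For Day 29-85, 21 days with CV 20% gives −2.9%, and 25 days with CV 30% gives −15.4%.

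**Step 3: adding assay error and the r² rule.** Log-linear fits were simulated on the scheduled days with 15% residual error and adjusted r² ≥ 0.8, at CV 30% and for Day 29-85. At a geometric mean of 21 days the mean fell from 21.8 to 19.4 days (−10.9%, 16.5% dropped). At 28 days it fell from 28.7 to 22.2 (−22.7%, 44.8% dropped). No setting gave an upward bias.

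**Step 4: windows that differ between subjects.** If the last quantifiable sample is Day 43, a fit from Day 15 covers 28 days and the cap falls to 14 days. A simulation ended each window at the first concentration below the assay limit (Day 8 concentration about 10 times that limit, geometric mean 21 days, CV 25%). It dropped 25% of values, from 14 days upward. The dropped values averaged 25.2 days and the kept ones 21.3, against 22.3 for all.

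**The case against.** Span ≥ 2 is a prespecified reliability filter: a half-life fitted over less than two half-lives is imprecise, and keeping it has a cost. Nothing is hidden. Failing values are listed and flagged, the regression range, span and adjusted r² are listed for each subject, and n is shown by dose, so the unfiltered mean can be rebuilt. No hypothesis test or primary endpoint rests on half-life. All of this stands. It keeps the point minor, but it does not correct the table, whose mean, median and maximum remain truncated.

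A reader might infer four stronger things that the documents do not support.

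- *That bias will occur.* No half-life is given. At 14 days the effect is under 1% unless the window is as short as Day 43-85.
- *That follow-up is fixed at Day 85.* Day 120 is optional and depends on a sponsor recommendation, but where it is sampled most of the effect disappears. A terminal phase that can be fitted from Day 8 also shrinks it.
- *That the rule always removes the longest half-lives.* This is strictly true only for a common window. With subject-specific windows, or windows cut short by the assay limit, moderate half-lives can fail too.
- *That dose comparisons or dosing intervals are at stake.* No between-dose comparison of half-life is planned, since dose proportionality uses Cmax and AUC only. The stated later use is dose selection and power, not dosing interval. Shorter windows at low doses are plausible, but the documents do not show them.

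**Conclusion.** The point holds in conditional form. The cap at half the window is certain from the SAP's own definitions. For a common window the direction is downward whenever any value is removed, and it stayed downward when simulated windows were shortened by the assay limit.

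The size rests on an assumed lognormal half-life with mean 14-28 days and CV 20-30%. It runs from under 1% (14 days with a window of 56 days or more, and most cases with Day 120), through about 8-9% (21 days with CV 30%, or 25 days with CV 20%, Day 29-85), to 21% (28 days, CV 30%, Day 29-85). It is larger only if the three-point minimum window is used. Nothing in the documents says where in that range the trial will fall.

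This reads the exclusion as applying to half-life on the span criterion. The SAP wording could also be taken to reach adjusted r², or CL, Vd and AUC to infinity. This is a worthwhile reporting improvement, not a threat to the study's conclusions.

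**What to change.** In SAP 9.1.2.1 and 9.1.1:

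- Keep the span flag and the summary restricted to span ≥ 2.
- Add a half-life row by dose for all subjects with at least 3 terminal points and adjusted r² ≥ 0.8, whatever the span.
- Report the number and percentage failing span by dose, as is already planned for extrapolated AUC above 20%.
- State which criterion and which parameters the exclusion covers.

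The cost is one summary row, one count and a sentence of clarification, with no new data. The downside is that the added row includes less precise individual half-lives, which is why the restricted row should stay beside it.
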